13.4.3 Photopic Binocular DCIVA

Phase I/Pilot subjects will be excluded from the analysis of this endpoint.

Photopic binocular DCIVA (logMAR) at 66 cm at Post-Operative Visit 4 (Day 120 to 180 after second eye IOL implantation) will be analyzed using an ANCOVA with DCIVA as the dependent variable and treatment and site as fixed factors. The treatment effect (LS mean for Test group IOL minus LS mean for Control group IOL) will be estimated in addition to a two-sided 90% CI. The analysis will be based on observed data for ITT, mITT, and PP sets. Multiple imputation of missing data will not be applied.

13.4.4 Photopic Binocular UCIVA

Phase I/Pilot subjects will be excluded from the analysis of this endpoint.

Photopic binocular DCIVA (logMAR) at 66 cm at Post-Operative Visit 4 (Day 120 to 180 after second eye IOL implantation) will be analyzed similarly to the analyses of the second primary effectiveness endpoints described in [Section 13.3.2](#) using a seed of 1303271003 for imputation of missing data.

13.4.5 BCDVA, DCNVA, and DCIVA

First eye BCDVA, DCNVA, and DCIVA evaluated at Post-Operative Visit 5 (Day 330 to 420 after second eye IOL implantation) will be summarized descriptively using continuous summary statistics by treatment.

13.5 Supportive Effectiveness Analyses

13.5.1 Visual Acuity in Phase I/Pilot Subjects

Phase I/Pilot subjects will be excluded from the primary summaries of all the outcomes related to near and intermediate VA and will be summarized separately. Missing data will not be imputed.

The VA continuous effectiveness endpoints included in [Section 3.2.5](#) will be summarized descriptively using continuous summary statistics by treatment assignment, eye, distance, and visit.

13.5.2 Categorical Analysis of Visual Acuity

For all corrected and uncorrected visual acuity endpoints at Post-Operative Visit 4 (Day 120 to 180 after second eye IOL implantation), logMAR value will be converted to Snellen equivalent. Percentages of eyes that achieve VA in Snellen equivalent for each category in both mutually exclusive (20/10, 20/12.5, ..., 20/200, worse than 20/100) and cumulative categories (20/200 or better, 20/160 or better, ..., 20/12.5 or better) for first eyes, second eyes, and all eyes will be summarized by treatment group.

Categorical summaries will use the logMAR to Snellen conversion values as shown in Table 5.

Table 5. logMAR to Snellen Equivalent Conversion

logMAR Value, Rounded to the Nearest 0.1	Snellen Equivalent
Missing	Missing
-0.3	20/10
-0.2	20/12.5
-0.1	20/16
0.0	20/20
0.1	20/25
0.2	20/32
0.3	20/40
0.4	20/50
0.5	20/63
0.6	20/80
0.7	20/100
0.8	20/125
0.9	20/160
1.0	20/200
> 1.0	Worse than 20/200

The following rates will be also provided by treatment randomized for the mITT set; and for first eyes, second eyes, and all eyes where applicable:

- Rate of loss of visual acuity of 0.2 logMAR or more from Preoperative Visit 0A/B (Day -30 to -5) to post-operative Visit 4 in UCDVA
- Rates of loss of visual acuity of 0.2 logMAR or more from Preoperative Visit 0A/B (Day -30 to -5) to post-operative Visit 4 in BDCVA

Visual acuity data will be presented in a data listing. In addition, BCDVA of ≥ 0.3 logMAR and visual acuity data with a loss of at least 0.2 logMAR in UCDVA and BDCVA will be presented separately in data listings.

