## **13.5.3 Primary Effectiveness Analyses**

### **13.5.3.1 Photopic Monocular BCDVA**

Photopic monocular BCDVA in first eyes will be assessed at Post-Operative Visit 4 using the methods described in [Appendix B](#) on Methods of Clinical Evaluation. The total number of letters correct will be entered into the electronic case report form.

The number of letters correct will be converted to logMAR units using the following equation:

$$\text{logMAR BCDVA} = 1.7 - 0.02 \times \text{letters correct}$$

Photopic monocular logMAR BCDVA in first implanted eyes at Post-Operative Visit 4 will be summarized using continuous summary statistics by treatment group for the mITT Set. Imputation of missing data is not conservative in non-inferiority testing. Therefore, missing data will not be imputed for the BCDVA non-inferiority test. A statistical model will be constructed with BCDVA as the dependent variable and treatment and site as fixed factors. The treatment effect (least squares mean Test group IOL VA minus least squares mean Control group IOL VA) in logMAR units will be estimated in addition to a two-sided 90% confidence interval. If the upper confidence limit (equivalent to a one-sided upper 95% confidence limit for the treatment effect) is less than 0.1, then the Test lens will be statistically non-inferior to the control lens.

The previous continuous summary statistics will also be provided for the Per Protocol Set. However, non-inferiority will not be evaluated with the PP Set and statistical success will not depend upon the results of the PP analysis.

BCDVA at Visit 4 for the Test group will be summarized categorically (20/20 or better, 20/25 or better, 20/32 or better, 20/40 or better, and worse than 20/40) for the mITT and Best Case Sets. Two-sided exact binomial 90% confidence intervals around the proportions of eyes 20/40

or better will be presented. Categorical summaries will use whole line binning as shown in the following logMAR to Snellen conversion table ([Table 3](#)):

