**Table 3. logMAR to Snellen Conversion Table**

logMAR Value	Snellen Value
$\leq 0.00$	20/20 or better
$\leq 0.10$	20/25 or better
$\leq 0.20$	20/32 or better
$\leq 0.30$	20/40 or better
$> 0.30$	Worse than 20/40

For the analyses of the mITT and Best Case Sets, one-sided exact binomial tests comparing the proportion of Multifocal IOL eyes with BCDVA 20/40 or better to the relevant control rate (92.5% for all eyes and 96.7% for best case eyes) will be performed and p-values will be presented. If the p-value is less than or equal to 0.05, then the null hypothesis will be rejected.

If the null hypothesis is not rejected for the mITT and Best Case Sets in the primary analyses, then it will be concluded that the Multifocal IOL is statistically successful in this outcome.

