9.5 Visit Window

For analysis of data by visit, only in-window visit data will be included in the analysis of a scheduled visit's data. If a scheduled visit is completed outside of the prescribed visit window, then the visit and its window will be handled as follows:

- The out-of-window scheduled visit will be reclassified as an interim (unscheduled) visit.
- If one or more unscheduled visits occurred in the window, then the unscheduled visit that occurred closest to the center of the visit window will be reclassified as the in-window (scheduled) visit.
- If two unscheduled visits occurred in the visit window, are the closest visits to its center, and are equidistant from its center, then the later of the two visits will be reclassified as the in-window (scheduled) visit.

9.6 logMAR Calculation

The following effectiveness data will be assessed as letters read correctly (letters correct) or as count fingers (CF), hand motion (HM), light perception (LP), or no light perception (NLP):

- Photopic monocular/binocular UCDVA
- Photopic monocular/binocular BCDVA
- Photopic monocular/binocular UCNVA
- Photopic monocular/binocular DCNVA
- Mesopic monocular/binocular DCNVA
- Photopic monocular/binocular UCIVA
- Photopic monocular/binocular DCIVA
- Mesopic monocular/binocular DCIVA
- Binocular BCDVA Defocus Curves
- Photopic monocular BCDVA (simulated astigmatism)
- Photopic monocular DCNVA (simulated astigmatism)
- Photopic monocular DCIVA (simulated astigmatism)

The logMAR VA for the data listed above will be computed as follows for subjects who can read at least one letter.

$$\text{logMAR VA} = 1.70 - (0.02 \times \text{letters read correctly})$$

Subjects who cannot read any letters but who can count fingers will be assigned a logMAR VA value of 2.00. Subjects who cannot read any letters but who can perceive hand motion will be assigned a logMAR VA value of 2.30. Subjects who cannot perceive hand motion will be assigned a logMAR VA value of missing.

For UCDVA and BCDVA data, logMAR score will be captured in the Electronic Data Capture (EDC) database. The scores will not be pulled from EDC database directly.

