13.3.1 Photopic Monocular BCDVA

Photopic monocular BCDVA (logMAR) in first eyes at Post-Operative Visit 4 (Day 120 to 180 after second eye IOL implantation) will be summarized using continuous summary statistics by treatment group. Imputation of missing data is not conservative in non-inferiority testing. Therefore, missing data will not be imputed for the BCDVA non-inferiority test. An analysis of covariance (ANCOVA) model will be constructed with BCDVA as the dependent variable and treatment and site as fixed factors. The treatment effect (least squares [LS] mean for Test group IOL minus LS mean for Control group IOL) will be estimated in addition to a two-sided 90% CI. If the upper confidence limit (equivalent to a one-sided upper 95% confidence limit for the treatment effect) is less than 0.1, then the Test lens will be statistically non-inferior to the control lens. The summary and analysis will be performed for both ITT and mITT Sets.

The previous continuous summary statistics will also be provided for the PP Set. However, non-inferiority will not be evaluated with the PP Set, and statistical success will not depend upon the results of the PP analysis.

The BCDVA at Post-Operative Visit 4 (Day 120 to 180 after second eye IOL implantation) for the Test group will be summarized categorically (20/20 or better, 20/25 or better, 20/32 or better, 20/40 or better, and worse than 20/40) for the ITT, mITT, and Best Case Sets. Two-sided exact binomial 90% CIs around the proportions of eyes 20/40 or better will be presented. Categorical summaries will use whole line binning as shown in Table 4.

Table 4. logMAR to Snellen Conversion Table

logMAR Value	Cumulative Snellen Category
≤ 0.00	20/20 or better
≤ 0.10	20/25 or better
≤ 0.20	20/32 or better
≤ 0.30	20/40 or better
> 0.30	Worse than 20/40

For the analyses of the ITT, mITT, and Best Case Sets, one-sided exact binomial tests comparing the proportion of Multifocal IOL eyes with BCDVA 20/40 or better to the relevant control rate (92.5% for all eyes in ITT and mITT Sets and 96.7% for Best Case Set eyes) will be performed, and p-values will be presented. If the p-value is less than or equal to 0.05, then the null hypothesis will be rejected. Similar analysis will be performed for first eyes and second eyes as supportive analysis.

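### SAP Table 5 rounds logMAR to the nearest 0.1, so supportive Visit 4 BCDVA summaries count 0.32 and 0.34 as 20/40, while SAP Table 4 and protocol Table 3 class them as worse than 20/40

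*SAP*

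**What the plan says.** Protocol 13.5.3.1 (BCDVA) and SAP 13.3.1 (BCDVA) use the same classification:

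- Protocol: "Categorical summaries will use whole line binning as shown in the following logMAR to Snellen conversion table". That table (Table 3) sets 20/40 or better at logMAR 0.30 or less and labels anything above 0.30 "Worse than 20/40".
- SAP: "Categorical summaries will use whole line binning as shown in Table 4". The last row of Table 4 reads "> 0.30 Worse than 20/40". Neither table rounds first.

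The exact binomial tests against 92.5% and 96.7% sit in this same SAP section.

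SAP 13.5.2 then gives a different rule: "Categorical summaries will use the logMAR to Snellen conversion values as shown in Table 5". The first column of Table 5 is headed "logMAR Value, Rounded to the Nearest 0.1", and 0.3 maps to 20/40. The section applies to all Visit 4 acuities, corrected and uncorrected, for first eyes, second eyes and all eyes, in both mutually exclusive and cumulative Snellen categories. Monocular BCDVA is not exempted, and neither table is given precedence. SAP section 16 lists three changes from the protocol, all about the analysis population for the primary safety analyses. The rounding in Table 5 is not among them.

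**The concern.** One acuity, at one visit and in the same eyes, is assigned to Snellen lines by two rules that disagree, and the output label is the same. A programmer who follows the SAP literally will produce two percentages headed 20/40 or better for first-eye BCDVA in the Test group: one from 13.3.1 and one from 13.5.2. The second departs from the protocol's BCDVA cut-off without being declared. Because the rounding rule can only move an eye to the same or a better line, the discrepancy always runs in one direction. At stake is the consistency of the reported BCDVA categories, and the risk that a reader quotes the rounded rate as if it were the protocol-defined one.

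**Working it through.** The plan states no figure to reproduce here, so the check is to score each possible value under both rules.

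**Inputs**

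- Conversion, SAP 9.6 and protocol 13.5.3.1: logMAR = 1.70 − 0.02 × letters. Values fall on a grid of 0.02.
- Rule A, SAP Table 4 and protocol Table 3: unrounded cut-offs at 0.00, 0.10, 0.20 and 0.30.
- Rule B, SAP Table 5: round to the nearest 0.1, then read the line.
- SD 0.15 and 300 Test eyes, from the BCDVA non-inferiority calculation in SAP 6.4.
- Mean BCDVA: not given in the documents, so 0.00, 0.05 and 0.10 are assumed.

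**Step 1: scores around the 20/40 line**

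| Letters | logMAR | Table 4 / protocol Table 3 | Table 5 |
|---|---|---|---|
| 70 | 1.70 − 1.40 = 0.30 | 20/40 | 20/40 |
| 69 | 1.70 − 1.38 = 0.32 | worse than 20/40 | 20/40 |
| 68 | 1.70 − 1.36 = 0.34 | worse than 20/40 | 20/40 |
| 67 | 1.70 − 1.34 = 0.36 | worse than 20/40 | 20/50 |

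The effective limit for 20/40 or better is 0.30 (at least 70 letters) under Table 4 and 0.34 (at least 68 letters) under Table 5.

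**Step 2: the other lines in Table 4**

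| logMAR | Table 4 | Table 5 |
|---|---|---|
| 0.22, 0.24 | 20/40 | 20/32 |
| 0.12, 0.14 | 20/32 | 20/25 |
| 0.02, 0.04 | 20/25 | 20/20 |

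Each line shifts by two letter scores, always to the better category. A rounding tie would need a value such as 0.25 or 0.35, and none lies on the 0.02 grid. The result therefore does not depend on how ties are programmed.

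**Step 3: size at the 20/40 line**

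Treat BCDVA as normal with mean μ and SD 0.15, recorded on the 0.02 grid. The rate under Table 4 is Φ((0.31 − μ)/0.15) and under Table 5 is Φ((0.35 − μ)/0.15), with the limits placed half a grid step above 0.30 and 0.34.

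| Assumed mean | Table 4 | Table 5 | Gap (points) | Eyes of 300 |
|---|---|---|---|---|
| 0.00 | Φ(2.067) = 98.1% | Φ(2.333) = 99.0% | 1.0 | 2.9 |
| 0.05 | Φ(1.733) = 95.8% | Φ(2.000) = 97.7% | 1.9 | 5.6 |
| 0.10 | Φ(1.400) = 91.9% | Φ(1.667) = 95.2% | 3.3 | 9.9 |

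Gaps are taken before rounding the rates.

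**The case against.** The strongest reply is that nothing decisive depends on Table 5. It belongs to the supportive effectiveness analyses, is descriptive, and has no hypothesis or success criterion. That stands, and it limits the point in several ways.

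- A reader might infer that the ISO success decision is at risk. With 300 eyes the 92.5% test rejects at 269 eyes at 20/40 or better (p = 0.045) and passes at 270 (p = 0.067), so one reclassified eye could put the two rates on opposite sides of that limit. The documents do not support the inference: 13.3.1 fixes Table 4 for the test, and 13.5.2 tests nothing. The rate listed as item 18 in SAP 3.2.5 names no table, but its closest match is also 13.3.1.
- A reader might infer that the SAP departs from the protocol for every acuity. It does not. The protocol states whole-line binning only for monocular BCDVA. It sets no Snellen rule for near, intermediate or uncorrected acuity, so Table 5 contradicts nothing there. Table 4 also has no cut-offs beyond 20/20 to 20/40.
- A reader might infer larger gaps. The same formula gives 10.4 points at a mean of 0.30 and 7.7 at 0.45. Those means are implausible for BCDVA, where inclusion criterion 4 requires a projection better than 20/32. For near or intermediate acuity no second, Table 4 rate is planned.
- Defocus summaries (SAP 13.5.3) cite Table 4, not Table 5, and are outside this point.

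It is also fair that the rounding is applied identically in both arms, so no known bias in the between-arm difference follows. What the reply does not remove is the overlap in scope: BCDVA falls under both sections, with no text to choose between them.

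**Conclusion.** The inconsistency is real and confined to the supportive BCDVA summaries. As written, the SAP yields two rates labelled 20/40 or better for Visit 4 BCDVA, and the Table 5 rate is equal or higher. The gap is about 1 to 3 percentage points for assumed means of 0.00 to 0.10 with SD 0.15 and approximate normality. It is zero if no eye reads 68 or 69 letters. SAP 13.5.2 does not name an analysis set for these percentages. The statement that the same eyes are counted twice assumes it uses a set that 13.3.1 also uses, such as mITT. The primary endpoint, its reference rates and its test are unaffected.

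**What to change.** In SAP 13.5.2, classify BCDVA with the unrounded cut-offs of Table 4 and protocol Table 3: 20/40 or better is logMAR ≤ 0.30, 20/32 or better ≤ 0.20, 20/25 or better ≤ 0.10, and 20/20 or better ≤ 0.00.

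Preferably extend the same unrounded whole-line rule to the remaining Table 5 lines and to the other acuities, so that the report uses one convention. Neither document gives cut-offs for those lines, so this is a choice to be written into the table. If the sponsor prefers to keep rounding for the other acuities, label the Table 5 summaries as rounded and exclude BCDVA from them.

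The cost is an edit to one SAP table and its introductory sentence, with slightly less favourable supportive rates. No new data are needed, and the primary test does not change.

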13.5.3 Binocular Defocus Curves

Assessment

Defocus curves will be assessed binocularly at the Post-Operative Visit 4 (Day 120 to 180 after second eye IOL implantation) under photopic conditions and may be assessed at unscheduled visits. Defocus powers will be +1.50 D to -3.50 D in 0.5 D increments, except in the range of +0.50 D through -0.50 D, which will be in 0.25 D increments. Subjects will be selected in three photopic pupil size groups as measured at Post-Operative Visit 4 (Day 120 to 180 after second eye IOL implantation): small (less than 3.0 mm); medium (at least 3.0 and no more than 4.0 mm); and large (greater than 4.0 mm).

The number of letters read correctly under each testing condition will be recorded in the electronic Case Report Form.

Preprocessing

Letters read correctly will be converted to logMAR units and to Snellen equivalent prior to summarization.

Tables

The results at Post-Operative Visit 4 (Day 120 to 180 after second eye IOL implantation) will be summarized continuously (logMAR) and discretely in both the mutually exclusive Snellen categories shown in Table 4 and in cumulative Snellen categories from 20/20 or better through 20/100 or better and worse than 20/100 by defocus lens power and treatment group for subjects in sub-study in a table. In addition, these summaries will be provided by pupil size (small [< 3.0 mm], medium [$3.0 - 4.0$ mm], large [> 4.0 mm]) and by axial length (short [< 21.0 mm], medium [$21.0 - 26.0$ mm], and large [> 26.0 mm]).

Listing

Defocus curve data will be provided for all subjects in the sub-study in a listing. The listing will display the subject number, treatment group, visit (Post-Operative Visit 4 (Day 120 to 180 after second eye IOL implantation), Unscheduled), visit date, OD and OS pupil sizes (mm), axial length, defocus power (D), letters correct, logMAR visual acuity, and Snellen equivalent. The listing will be sorted by subject number in ascending order and, within subjects, by visit date in ascending order and, within visit date, by defocus power in descending order.

Figures

Defocus curves will be plotted in figures for subjects in sub-study at Post-Operative Visit 4 (Day 120 to 180 after second eye IOL implantation) and, separately, by pupil size (small, medium, large). Mean logMAR VA versus defocus lens power (D) will be plotted with the two treatment arms overlaid in each defocus curve plot.

The vertical axis will be labeled “Mean logMAR Visual Acuity.” Vertical axis tick marks will be displayed at 0.1 logMAR intervals in descending order (e.g., 1.0 at the bottom and -0.1 at

the top). Each vertical axis tick mark will be labeled with both the logMAR and, in parentheses, Snellen values (e.g., “0.5 (20/63)”).

The horizontal axis will be labeled “Defocus Lens Power (D).” Horizontal axis tick marks will be in descending order (+1.50 D on the left and -3.50 D on the right) at 0.50 D intervals. The horizontal tick mark labels will be displayed to one decimal place.

Defocus curves will be interpolated between the plotted points using SAS® software’s cubic spline method invoked by the statement INTERPOL = SPLINE in the SYMBOL statement (or a similar method). Horizontal and vertical grid lines will be included at each tick mark level.

14 Additional Clinical Parameters

14.1 Slit-Lamp Biomicroscope Examination

Slit-lamp biomicroscope examination results will be summarized categorically by treatment received and visit for first eyes, second eyes, and all eyes separately for the Modified Safety Set:

- Lid (not clinically significant [NCS], mild, moderate, severe, very severe)
- Conjunctiva
 - Normal
 - Abnormal (Hyperemia: none, mild, moderate, severe, very severe)
- Conjunctiva additional abnormalities (NCS, mild, moderate, severe, very severe)
- Superficial punctate keratopathy (none, mild, moderate, severe, very severe)
- Corneal wound edema (none, mild, moderate, severe)
- Cornea stromal edema (none, mild, moderate, severe)
- Cornea additional (NCS, mild, moderate, severe, very severe)
- Anterior chamber cells (0, 0.5+, 1+, 2+, 2+, 4+)
- Anterior chamber flare (0, 1+, 2+, 3+, 4+)
- Anterior additional (NCS, mild, moderate, severe, very severe)
- Iris/Pupil (Normal, Abnormal)
- Iris/Pupil abnormalities (NCS, mild, moderate, severe, very severe)
- Cataract density (slight [1+], moderate [2+], dense [3+], very dense [4+]), collected at pre-operative visit only

Slit-lamp biomicroscopy examination data will be presented in a data listing.

14.2 Manifest Refraction

Prior to analysis, categorization, and presentation, refraction results will be converted to negative cylinder notation by application of the following steps in order.

1. If the cylinder is missing, then the negative cylinder notation sphere, cylinder, and axis will all be missing.
2. If the non-missing cylinder is less than or equal to zero, then the refraction results are already in negative cylinder notation and will not be changed.

3. If the cylinder is greater than zero, then the following steps will be completed
 - a. The sphere in negative cylinder notation will equal the sum of the positive cylinder notation sphere and cylinder.
 - i. However, if the positive notation sphere is missing then the negative cylinder notation sphere will also be missing.
 - b. The negative cylinder notation cylinder will equal the negative of the positive cylinder notation cylinder
 - c. The negative cylinder notation axis will equal the positive cylinder notation axis rotated by 90 degrees, with necessary adjustments to ensure that the resulting axis is within the interval from 1 to 180 degrees, inclusive.
 - i. If the positive cylinder notation axis is missing, then the negative axis notation cylinder will also be missing.

Summaries will be by treatment received and visit for the Modified Safety Set for first eyes, second eyes, and all eyes separately.

Sphere (D), cylinder (D), and spherical equivalent (D) will be summarized using continuous summary statistics. In addition, proportion of eyes with difference between intended spherical equivalent and achieved spherical equivalent within +/- 0.50 D and within +/- 1.00 D will be summarized using categorical statistics.

Axis will be summarized using continuous and categorical (none, with-the-rule, oblique, against-the-rule) summary statistics using the following definitions.

- None: 0°
- With-the-rule: 1° to 30° or 150° to 180°
- Oblique: 31° to 59° or 121° to 149°
- Against-the-rule: 60° to 120°

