## 10.0 CHORD LENGTH $\mu$ AND KERATOMETRY

Chord length  $\mu$  measurements will be recorded at the Pre-Operative Visit, Visit 4 and Visit 5 using either IOL Master or LENSTAR. Chord length  $\mu$  measurements will be regarded as an adequate surrogate for angle kappa measurements.

Keratometry values at the Pre-Operative Visit which are required for eligibility and IOL power calculations, as well as keratometry values at Post-Operative Visits 3, 4 and 5, may be obtained from automated keratometry (e.g., IOL Master or LENSTAR) or simulated keratometry (e.g., topography, Scheimpflug photography or optical coherence tomography). Note that the steep and flat axes which are reported should be orthogonal. The same method should be used for a specific subject/eye throughout the study.

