6.7 Overall Sample Size and Adjustment for Dropouts

The sample size of 300 study lens group subjects and 150 control group subjects is specified in ANSI Z80.12-2007 (R2012) and ISO 11979-9:2006. Moreover, ISO 11979-7 specifies that a minimum of 300 subjects should complete a clinical evaluation of an IOL.

To allow for losses of up to 10%, approximately $[300/(1 - 0.1)] = 334$ Test group subjects and approximately $[150/(1 - 0.1)] = 167$ Control group subjects will be enrolled.

7 Output Data and Data Analysis Convention

The following reporting conventions will be used:

All data will be provided in data listings sorted by the study center, subject number, and visit will be presented in all listings, when applicable. Listings will be presented for all randomized subjects unless otherwise specified.

Descriptive statistics will include: number of non-missing values (n), mean, median, SD, minimum, maximum for continuous variables, and n (%) for categorical variables. The mean, median, and the upper and lower limits of the CI for the mean will be displayed to one more decimal place than the original data or derived analysis data. The SD values will be displayed to two more decimal places than the original data. The minimum and maximum will be displayed to the same number of decimal places as the original data.

The number and percentage of responses will be presented in the form XX (XX.X), 0, or XXX (100) unless specified otherwise, where the percentage is in parentheses. The denominator of all percentages will be number of subjects in the analysis population, unless otherwise stated. When count data are presented, the percent will be suppressed when the count is zero in order to draw attention to the non-zero counts. A row denoted “Missing” will be included in count tabulations where necessary to account for dropouts and missing values. Non-zero percentages will be rounded to one decimal place, except 100% will be displayed without any decimal places.

Differences between treatment groups will be calculated as test IOL minus control IOL. All analyses will be conducted using SAS® Version 9.4.

8 Analysis Populations

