14.11 Keratometry

The actual values and change from Preoperative Visit 0A/B (Day -30 to -5) values in the following keratometry parameters will be summarized using continuous statistics by treatment received and by visit for the Modified Safety Set for first eyes, second eyes, and all eyes:

- Steep power (D)
- Steep axis ($^{\circ}$)
- Flat power (D)
- Flat axis ($^{\circ}$)

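### Refraction and keratometry axes wrap at 180°/1° but are summarised as ordinary numbers, so axis statistics mislead wherever eyes straddle the wrap (descriptive tables only)

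*SAP*

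**What the plan says.** **Refraction.** SAP 14.2 converts refractions to minus-cylinder form, "with necessary adjustments to ensure that the resulting axis is within the interval from 1 to 180 degrees, inclusive". It then states: "Axis will be summarized using continuous and categorical (none, with-the-rule, oblique, against-the-rule) summary statistics using the following definitions". The definitions include "With-the-rule: 1° to 30° or 150° to 180" degrees and "Against-the-rule: 60° to 120" degrees, and they label 0° as no axis. The section plans no change from the preoperative visit for axis.

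**Keratometry.** SAP 14.11 states: "The actual values and change from Preoperative Visit 0A/B (Day -30 to -5) values in the following keratometry parameters will be summarized using continuous statistics". The list of parameters is steep power, steep axis, flat power and flat axis. Protocol Appendix B, section 10.0, adds: "Note that the steep and flat axes which are reported should be orthogonal".

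**Meaning of continuous statistics.** SAP section 7 (output conventions) states: "Descriptive statistics will include: number of non-missing values (n), mean, median, SD, minimum, maximum for continuous variables".

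Neither document mentions axial statistics, vector components or wrapping of differences. The table of changes in SAP section 16 does not touch the point.

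**The concern.** SAP 14.2 already treats axis as circular in two ways: it returns rotated axes to the 1° to 180° range, and it joins the two ends of that range into one with-the-rule class. It then passes the same numbers to a linear mean, median and SD, which treat 1° and 180° as 179° apart. Within one table, the numeric and categorical summaries of the same eyes can therefore state opposite orientations.

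For keratometry, SAP 14.11 also subtracts axes between visits. No axis can turn by more than 90°, because a larger turn is the same as a smaller one the other way, yet plain subtraction can return values up to 179° in size. What is at stake is the accuracy of descriptive tables, which would contain entries that an ophthalmic reader would recognise as impossible.

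**Working it through.** The documents give no axis mean, axis change or axis spread, so there is no stated figure to reproduce. The check sets the planned rule against axial statistics.

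**Formulas**
- Planned: arithmetic mean, median and SD of axis; change = post − pre.
- Axial mean: half of atan2(mean of sin 2θ, mean of cos 2θ), modulo 180°.
- Wrapped change: ((post − pre + 90) mod 180) − 90.

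**Worked examples**
- Axes 5° and 175°: planned mean (5 + 175)/2 = 90°, median 90°, SD 120°. The axial mean is 180°. Both eyes are with-the-rule under SAP 14.2; the planned mean falls in its against-the-rule class.
- Axes 1° and 180°: planned mean 90.5°, axial mean 0.5°.
- Change from 178° to 2°: planned 2 − 178 = −176°. Wrapped: (−176 + 90) mod 180 = 94, and 94 − 90 = +4°.
- Change from 175° to 5°: planned −170°, wrapped +10°.

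**Simulation of axis values.** The spreads are assumptions. Axes are coded as whole degrees from 1 to 180.
- Centred on 180°, SD 10° to 20°: planned mean 92° to 94°, planned SD 75° to 82°, axial mean 180°.
- Centred on 90°, same spreads: planned mean 90°, planned SD equal to the true spread.

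The planned mean thus lands near 90° for either orientation and cannot tell them apart.

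**Simulation of axis change (keratometry only).** The spread around each centre is 15°.

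| Population | True rotation SD | Planned change SD | Eyes with change beyond 90° |
|---|---|---|---|
| All near 180° | 10° | 73° | 19% |
| All near 180° | 5° | 56° | 10% |
| 70% near 180°, 20% near 90°, 10% uniform | 5° | 47.5° | 7.4% |
| 50% near 180°, 40% near 90°, 10% uniform | 5° | 40.5° | 5.4% |
| 30% near 180°, 60% near 90°, 10% uniform | 5° | 31.7° | 3.2% |

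In every row the wrapped change recovers the true SD. For an axis centred on 90° with these spreads, almost no eye reaches the wrap and the planned change is correct. With all axes near 180° and no systematic rotation, the planned mean change stayed between −1.1° and +0.1°, because crossings in the two directions nearly cancel. The SD, minimum and maximum have no such protection.

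**Which keratometry table is hit.** Steep and flat axes should be orthogonal. If one clusters near 90°, the other lies at 180°, so one of the two axis tables is sound and the other is distorted. In a mixed population both are affected.

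**Zero cylinder.** SAP 14.2 labels axis 0° as no axis but does not exclude it from the continuous summary, so eyes without cylinder could enter the mean as 0°.

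**The case against.** The strongest case on the other side is about weight. SAP 3.2.7 lists keratometry and manifest refraction under other assessments. No hypothesis in SAP 3.3, success criterion, sample size or multiplicity step uses axis. Refractive cylinder, spherical equivalent, and steep and flat power are summarised separately and are unaffected. The categorical axis table in SAP 14.2 handles the wrap correctly, all data appear in listings, and SAP section 2 allows supplementary analyses. All of this stands, and it sets the weight at minor.

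It is also fair to say that the 73° figure is a worst case for a single axis clustered at the wrap. In a mostly with-the-rule population that would be the flat axis, not the steep one. This stands too, although the mixed populations still inflate the change SD six- to ninefold (31.7/5 to 47.5/5).

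Three stronger readings are tempting, and the documents do not support them.
- **That the keratometry change table is the plan's measure of surgically induced astigmatism and should show whether the arms were comparable.** SAP 14.11 states no such purpose, and neither document plans that comparison. Axis rotation without power could not measure it. In first eyes, Appendix C places the incision before extraction and randomisation follows extraction, so the incision precedes allocation.
- **That refraction axis change will be wrong as well.** SAP 14.2 plans no such change.
- **That every axis mean and change will be wrong.** The error is certain only for groups with axes on both sides of the wrap; clusters near 90° are summarised correctly.

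None of this defends the linear statistics themselves. The listings and categories let a reader spot the fault, but they do not correct the planned table entries.

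**Conclusion.** The plan is wrong as written, with minor weight. In any group with axes on both sides of 180°/1°, which the with-the-rule class implies, the planned mean, median and SD of axis do not describe the eyes. For keratometry, plain subtraction produces impossible changes beyond 90°, so the SD, minimum and maximum of change are wrong even where the mean cancels to near zero.

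The worked examples follow from the SAP's own definitions and need no assumption. The simulated sizes do rest on assumptions: the axis spread, the rotation SD and the mix of orientations are not in the documents. They range from no error (axis centred on 90°) to a change SD of 73° instead of 10° (axis centred on 180°). The study's effectiveness and safety conclusions are not affected.

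**What to change.** In SAP 14.2 and 14.11:
1. Drop the mean, median, SD, minimum and maximum of axis, and of axis change. The median must go too, because it fails in the same way. Keep the categorical table in 14.2.
2. Exclude zero-cylinder eyes (axis coded 0°) from any numeric axis statistic.
3. Summarise astigmatism by power vectors, J0 = −(C/2)cos(2 × axis) and J45 = −(C/2)sin(2 × axis). For refraction, C is the minus cylinder with its axis. For keratometry, C is flat minus steep power with the flat axis. Give changes from the preoperative visit for keratometry.
4. If an axis change in degrees is still wanted, wrap it to the range −90° to +90° before summarising.

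As a check, take two refractions with C = −1.00 D at 5° and 175°. Both have J0 = 0.5 × cos 10° = 0.492, and J45 is +0.087 and −0.087. The mean vector is (0.492, 0), which corresponds to axis 180°, as it should.

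The cost is SAP wording and slightly more derivation code. No new data are needed.
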